6.14.1. Extent of Exposure

Duration of exposure to study treatment will be summarized by treatment group for each of the 2 safety analysis populations (that is, Induction Safety and All Active Treatment Safety). For the treatment period of interest associated with each safety analysis population, exposure will be calculated as the time period length in years (see Section 6.1.1.1) with start and end dates described in Table AMAJ.6.3. The following periods will be used for calculations:

- For the Induction Safety Population, the Induction Period Interval will be used.
- For the All Active Treatment Safety Population, 1) for patients randomized to mirikizumab and secukinumab, the Induction and Maintenance Period Interval will be used; 2) for patients randomized to placebo and entering the Maintenance Period, the Maintenance Period Interval will be used.

Total patient-years (PY) of exposure will be reported for both safety analysis populations by treatment group (see Table AMAJ.6.2). Descriptive statistics will be provided for patient-weeks of exposure and the frequency of patients falling into different exposure ranges will be summarized:

- >0, ≥4 weeks, ≥8 weeks, ≥12 weeks, ≥16 weeks, ≥ 24 weeks, ≥32 weeks, ≥40 weeks, ≥48 weeks
- >0 to <4 weeks, ≥4 weeks to <8 weeks, ≥8 weeks to <12 weeks, ≥12 weeks to <16 weeks, ..., ≥48 weeks

Additional exposure ranges may be considered if necessary. No p-values will be reported in these tables as they are intended to describe the study populations, rather than test hypotheses about them.

6.14.2. Adverse Events

A treatment-emergent adverse event (TEAE) is defined as an event that first occurred or worsened in severity after baseline. The MedDRA Lowest Level Term (LLT) will be used in the treatment-emergent computation. The maximum severity for each LLT during the baseline period will be used as baseline. The treatment period will be included as postbaseline for the analysis. For events with a missing severity during the baseline period, it will be treated as ‘mild’ in severity for determining treatment-emergence. Events with a missing severity during the postbaseline period will be treated as ‘severe’ and treatment-emergence will be determined by comparing to baseline severity. For events occurring on the day of first taking study medication, the start times of the study treatment and AE will be used to determine whether the event was pre- versus posttreatment. If start time for the AE is missing, it will be assumed to have started in the later period.

Summary tables as described in [Table AMAJ.6.7](#) will be presented for the 2 safety populations/periods as indicated. Summary tables will include the number and percentage of patients reporting an event. For events that are gender-specific (as defined by MedDRA), the number of participants at risk will include only patients from the given gender. Comparisons will be performed using Fisher’s exact test. For document writing purposes, tests with 2-sided p-values less than 0.05 will be referred to as “having strong evidence for a treatment difference”, unless otherwise noted. However, p-values should not be over interpreted for these safety analyses. Except for prespecified hypotheses, they correspond to data-driven hypotheses and hence are only useful as a flagging mechanism.

For the 2 safety populations, the baseline period and postbaseline will be defined as follows:

- *Induction Safety Population*: The baseline period is the Screening Period. The postbaseline period will be the Induction Period.
- *All Active Treatment Safety Population*: The baseline period for patients randomized to mirikizumab and secukinumab during induction is the Screening Period. For patients randomized to placebo, the baseline events are those events which are ongoing at the time of the first injection with mirikizumab (that is, the baseline period is a moment in time). Two different postbaseline periods will be used:
 - For “all miri” and “all secu”, the All Active Treatment Periods will be used.
 - For “all miri + follow-up” and “all secu + follow-up”, the All Active Treatment and Follow-Up Periods will be used.

Table AMAJ.6.7. Summary Tables Related to Adverse Events

Analysis	Population
Overview of AEs	I, A
Summary of TEAE PTs by decreasing frequency	I, A
Summary of TEAE PTs occurring in $\geq 1\%$ of patients by decreasing frequency	I, A
Summary of TEAE PTs by decreasing frequency within SOC	I, A
Summary of TEAE PTs by maximum severity by decreasing frequency	I, A
Summary of SAE PTs by decreasing frequency	I, A
Summary of AEs leading to treatment discontinuation	I, A
Listing of SAEs	ITT
Listing of Deaths	All Entered Patients

Abbreviations: A = All Active Treatment Safety; AE = adverse event; I = Induction Safety; ITT = Intent-to-Treat; PT = preferred term; SAE = serious adverse event; SOC = System Organ Class; TEAE = treatment-emergent adverse event.

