5.1. Summary of Study Design

Study I6T-MC-AMAJ (AMAJ) is a Phase 3, multicenter, randomized, double-blind, placebo- and active-controlled, parallel-group, multi-period study in adult patients with moderate-to-severe plaque psoriasis. Approximately 1443 patients will be randomized to treatment groups involving different mirikizumab doses and regimens, placebo, or secukinumab. The study is comprised of 2 treatment periods (Induction and Maintenance), which together last for up to 52 weeks, followed by a 12-week Posttreatment Follow-Up Period.

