5.1.3. Blinded Maintenance Period (Week 16 to Week 52 [36 Weeks])

Patients who were randomly assigned at baseline to receive mirikizumab in the Blinded Induction Period were also randomly assigned to receive either 250-mg mirikizumab every 8 weeks (Q8W) SC or 125-mg mirikizumab Q8W SC in the Blinded Maintenance Period, with maintenance dosing starting at Week 16 and ending at Week 48. Patients who were randomized to placebo in the Blinded Induction Period will receive 250-mg mirikizumab SC every 4 weeks (Q4W) for Weeks 16 through 32 and 250-mg mirikizumab Q8W thereafter. Patients who were randomized to 300-mg secukinumab SC in the Blinded Induction Period will continue this treatment with Q4W dosing during the Blinded Maintenance Period, starting at Week 16 and ending at Week 48.

Throughout the study, patients will receive placebo, as appropriate, to maintain the study blind across treatment groups.

A discontinuation criterion has been included for patients in any treatment group who remain at or above their baseline static Physician's Global Assessment (sPGA) score at Week 16 (Visit 9) and Week 24 (Visit 11), or remain at or above their baseline Psoriasis Area and Severity Index

(PASI) score at Week 16 (Visit 9) and Week 24 (Visit 11), to ensure patients who have not shown any benefit from study treatment are offered alternative therapies.

At Week 52, patients have 1 of the following options:

- Enter Study I6T-MC-AMAH (AMAH), a long-term extension study in which patients receive 250-mg mirikizumab Q8W SC or 125-mg mirikizumab Q8W SC, OR
- Discontinue study treatment and complete Study AMAJ's 12-week Posttreatment Follow-Up Period.

[figure not shown]
Patients who discontinue early from the study for any reason during this period will stop treatment and continue to the ETV and then the 12-week Posttreatment Follow-Up Period.

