5.1.4. Posttreatment Follow-Up Period (12 Weeks)

Patients who do not enroll into Study AMAH or who discontinue early from Study AMAJ will complete the Posttreatment Follow-Up Period (Visit 801 and Visit 802) of Study AMAJ.

For patients who have entered the Posttreatment Follow-Up Period, psoriasis therapy with another agent(s), as determined appropriate by the investigator, is allowed.

[Figure AMAJ.5.1](#) illustrates the study design.

Abbreviations: LV = last study visit; miri = mirikizumab; Q4W = every 4 weeks; Q8W = every 8 weeks; SC = subcutaneous; V = visit; w = weeks; W = week.

* Option to enter Study I6T-MC-AMAJ or to enter the Posttreatment Follow-Up Period.

Note: At Week 0 (V2), patients will be randomized in a 4:4:4:1 ratio to one of the following induction and maintenance period treatments: a) 250-mg miri at Weeks 0, 4, 8, 12 followed by 250-mg miri SC Q8W starting at Week 16; b) 250-mg miri at Weeks 0, 4, 8, 12 followed by 125-mg miri Q8W starting at Week 16; c) 300-mg secukinumab at Weeks 0, 1, 2, 3, 4, followed by 300-mg secukinumab Q4W starting at Week 4; d) placebo at Weeks 0, 4, 8, 12, followed by 250-mg miri Q4W starting at Week 16 through Week 32 followed by Q8W thereafter. Patients will receive placebo to maintain the study blind across treatment groups as shown (patients receiving 125-mg miri will receive 1 placebo injection at weeks they receive miri and 2 placebo injections at other times shown). Dosing is via SC injection for all treatments in all periods.

Figure AMAJ.5.1. Illustration of study design for Clinical Protocol I6T-MC-AMAJ.

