Induction and Maintenance Periods*	ITT; Induction and Maintenance PPS	placebo/250 miri; 300 secu; 250 miri Q4W/125 miri Q8W; 250 miri Q4W/250 miri Q8W; Total miri/miri (Note: Total miri represents the combined treatments of 250 miri Q4W/125 miri Q8W and 250 miri Q4W/250 miri Q8W.)	250 miri Q4W/125 miri Q8W vs 300 secu; 250 miri Q4W/250 miri Q8W vs 300 secu (For efficacy/healthoutcome measures, the comparisons will be only conducted from Week 20 to Week 52)
All Active Treatment Periods	All Active Treatments Safety	placebo/250 miri; 300 secu; 250 miri Q4W/125 miri Q8W; 250 miri Q4W/250 miri Q8W; all miri (Note: all miri represents the combined treatments of placebo/250 miri, 250 miri Q4W/125 miri Q8W and 250 miri Q4W/250 miri Q8W.)	250 miri Q4W/125 miri Q8W vs 300 secu; 250 miri Q4W/250 miri Q8W vs 300 secu

Treatment Groups and Comparisons for Each Study Period and Analysis Population

Study Period	Analysis Population	Treatment Groups	Inferential Comparisons
All Active Treatment + Follow-up Periods	All Active Treatment Safety	300 secu + FUP; all miri + FUP (Note: the header with “+ FUP” is used to emphasize that the observations from Follow-up Period are included.)	
All Periods	ITT	For study disposition only: placebo/250 miri; 300 secu; 250 miri Q4W/125 miri Q8W; 250 miri Q4W/250 miri Q8W; Total miri/miri	
	Induction Safety Population	For hepatic plot only: Ever on miri; Never on miri	

Abbreviations: FUP = follow-up; ITT = intent-to-treat; miri = mirikizumab; PPS = per protocol set; Q4W = every 4 weeks; Q8W = every 8 weeks; secu = secukinumab.

* For some analyses based on response status at certain weeks (Week 16 or 24), only maintenance period will be used, and the placebo/250 miri treatment group might not be displayed.

Note: for immunogenicity analysis, 300 secu treatment group will be excluded, thus the comparisons involving 300 secu will not be conducted; also the outputs for the “All Active Treatment Period” and “All Active Treatment + Follow-up Periods” will be combined.

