Induction and Maintenance Periods	Use the definition of the start of the Induction Period.	Use the definition of the end of Maintenance Period.
Follow-up Period: All patients who had Visit 801 or 802 are considered to have entered the Follow-up Period.	The latest of the following dates: (1) after the end of the Induction Period as described above, (2) after the end of the Maintenance Period as described above	The last date of the last study visit and study disposition date
All Active Treatment Periods: All patients who are treated with mirikizumab or secukinumab are considered to have entered this period.	For mirikizumab and secukinumab induction treatment groups, use the definition of the start of Induction Period; For placebo/250 miri treatment group, use the definition of the start of Maintenance Period.	The latest of the following dates: (1) the end of the Induction Period, (2) the end of the Maintenance Period
All Periods (Induction + Maintenance + Follow-up Periods)	Induction period start date	The last date of the last study visit and study disposition date

^a Missing dose time will be imputed as the earliest time that is consistent with available data about dose time. For example, suppose the minutes are missing but hour is present; in this case, we would impute the minutes to be 0.

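### The All Active and All Active + Follow-up adverse event tables specify only crude percentages although planned time at risk differs between columns; add incidence per 100 patient-years

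*SAP*

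**What the plan says.** - **Summary measure.** SAP Section 6.14.2: "Summary tables will include the number and percentage of patients reporting an event". Section 6.14 specifies no exposure-adjusted incidence.
- **Columns.** Table AMAJ.6.2 shows placebo/250 miri as a separate column in the All Active row and also pools it: "all miri represents the combined treatments of placebo/250 miri, 250 miri Q4W/125 miri Q8W and 250 miri Q4W/250 miri Q8W". The row that adds follow-up has the columns "300 secu + FUP; all miri + FUP".
- **Start of the clock.** Table AMAJ.6.3, All Active Treatment Periods: "For placebo/250 miri treatment group, use the definition of the start of Maintenance Period". The mirikizumab and secukinumab induction groups start at Induction.
- **Planned length.** Section 5.1 describes Induction and Maintenance, "which together last for up to 52 weeks, followed by a 12-week Posttreatment Follow-Up Period". Section 5.1.3 gives Maintenance as 36 weeks from Week 16.
- **Who adds follow-up time.** Under Section 5.1.4, only patients who stop early or do not enter Study AMAH. During that time "psoriasis therapy with another agent(s), as determined appropriate by the investigator, is allowed".
- **Patient-years.** Section 6.14.1: "Total patient-years (PY) of exposure will be reported for both safety analysis populations by treatment group". The intervals named there are Induction, Induction plus Maintenance, and Maintenance. Follow-up is not among them.
- **Comparisons.** For the All Active population, Table AMAJ.6.2 lists only the two arms randomized to mirikizumab, each against secukinumab. The comparison cell of the + FUP row is empty.

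**The concern.** The percentage of patients with an event rises with time observed. Placing columns with different observation times side by side as n and % makes the shorter one look safer at the same underlying rate. This matters most for events that accrue over time, such as serious infections, malignancies and cerebro-cardiovascular events. Section 6.14.7 summarises these with the same baseline and postbaseline definitions.

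The placebo/250 miri column is short by design. The + FUP columns have a further problem: the share of patients adding 12 weeks may differ between drugs, and the plan computes no patient-years for that window. A reader of the + FUP table therefore has no denominator with which to correct the percentages. Patient-years are planned for the treatment intervals, but the plan does not use them as a denominator for adverse events.

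**Working it through.** **Inputs.** Total 1443 at 4:4:4:1, and arm sizes 888 (two mirikizumab arms), 444 and 111 (SAP Section 5.2). Planned weeks 52 and 36 (Sections 5.1 and 5.1.3). Follow-up 12 weeks (Section 5.1).

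**1. The plan's own figures.** 1443 × 4/13 = 444 and 1443 × 1/13 = 111, which reproduces the stated arm sizes. The documents state no figure for time at risk or for an adverse event rate.

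**2. Placebo/250 miri column.** Take an event with 10% risk over 52 weeks (illustrative) and the same constant hazard in every column. Over 36 weeks the expected percentage is 1 − 0.9^(36/52) = 7.0%. The relative shortfall is about 30%, with no difference in hazard.

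**3. Pooled all miri column.** Mean planned time is (888 × 52 + 111 × 36)/999 = 50.2 weeks, against 52 for secukinumab. The ratio is 50.22/52 = 0.966, or 3.4% shorter. For the same 10% event, the pooled column shows (888 × 10% + 111 × 7.03%)/999 = 9.67%. At a rate of 10 per 100 patient-years the two columns show 9.17% and 9.49%.

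**4. The + FUP columns.** Let f_m and f_s be the shares of mirikizumab and secukinumab patients who add 12 weeks. The time ratio is (50.22 + 12 f_m)/(52 + 12 f_s). The documents give neither share, so the following are assumptions:

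| f_m | f_s | All miri + FUP, weeks | 300 secu + FUP, weeks | Ratio |
|---|---|---|---|---|
| 10% | 10% | 51.42 | 53.2 | 0.967 |
| 30% | 30% | 53.82 | 55.6 | 0.968 |
| 10% | 30% | 51.42 | 55.6 | 0.925 |
| 30% | 10% | 53.82 | 53.2 | 1.012 |
| 5% | 50% | 50.82 | 58.0 | 0.876 |
| 50% | 5% | 56.22 | 52.6 | 1.069 |

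With equal shares the gap stays near 3%. With unequal shares it can widen or change sign. The formula adds follow-up to full planned treatment. Early discontinuers enter follow-up with less treatment time, so it is a simplification.

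**The case against.** The strongest reply is that no planned comparison uses the unequal columns. The two arms randomized to mirikizumab have the same 52 planned weeks as secukinumab, and they are the only All Active arms listed for comparison with it. The general Fisher's exact sentence in Section 6.14.2 names no further contrast, and the SAP treats these p-values as flags unless a hypothesis was prespecified. The pooled gap is about 0.3 percentage points for a 10% event. Exposure by group is reported under Section 6.14.1, so the shorter time is disclosed. Sections 6.14 and 6.14.7 also refer to compound level safety standards, which were not supplied and may contain rates. All of this stands. It makes the point one about descriptive displays and limits its weight. It does not supply a rate in Section 6.14.2 or a denominator for the + FUP columns.

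A reader might infer more than the documents support:

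- *That the + FUP table is the only safety summary reaching into follow-up.* It is not. The hepatic plot (Section 6.14.7.1) covers All Periods, and the note to Table AMAJ.6.2 combines treatment and follow-up outputs for immunogenicity.
- *That follow-up favours mirikizumab by design.* AMAH offers mirikizumab only, which could make entry differ by arm, but no entry shares are given and the sign can reverse (step 4).
- *That events after a switch to another agent make the safety results unattributable.* No rule stops the count when another psoriasis therapy starts, so such events fall in the + FUP window. But columns without follow-up are also planned and give the on-treatment view, and the + FUP header openly signals that follow-up is included. Censoring at a new therapy is a debatable choice, because it could remove delayed events.

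**Conclusion.** The concern holds as a low-cost improvement to descriptive tables. The clearest distortion is fixed by design: 7.0% shown for a 10% 52-week risk in the placebo/250 miri column. In all miri the design effect is small, 3.4% of planned time. In the + FUP columns the effect cannot be bounded in advance from the documents, in size or direction, which is a reason to prespecify a rate. A reader might take this as an invalid test of mirikizumab against secukinumab; the listed comparisons do not support that.

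The figures assume a constant and equal hazard, planned durations and no dropout. Placebo patients who never receive mirikizumab are outside the All Active population, and dropout in any arm will shift the actual times. The conclusion also assumes that the unseen safety standards do not already specify rates. If they do, Section 6.14.2 needs only to cite them, provided that they cover the + FUP window.

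**What to change.** 1. In Section 6.14.2, for the All Active and All Active + Follow-up summaries, add exposure-adjusted incidence per 100 patient-years beside n and %. Time at risk runs to the first event or the end of the period. Apply it to the TEAE overview, SAEs, adverse events of special interest and, for the on-treatment window, discontinuations due to an adverse event.
2. In Section 6.14.1, extend the patient-year calculation to include follow-up time for the + FUP columns.
3. Optionally, flag in the + FUP listings the events that start after the first non-study psoriasis therapy. Section 6.10 already works with medication start and stop dates. A censored analysis is not required.

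The cost is SAP wording, one extra column, and a time-at-risk derivation for each event summarised. The follow-up patient-years are new programming, because the current calculation stops at the treatment intervals. No endpoint, efficacy analysis or data collection changes.

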6.14.2.1. Common Adverse Events

The percentages of patients with TEAEs will be summarized by treatment using MedDRA PT for the common TEAEs (reported in $\geq 1\%$ before rounding of treated patients). Events will be ordered by decreasing frequency in the all treatment group. See [Table AMAJ.6.7](#).

6.14.2.2. Deaths, Other Serious Adverse Events, and Other Notable Adverse Events

The number and percentage of patients reported with an SAE during the treatment period will be summarized by treatment using MedDRA PT. Events will be ordered by decreasing frequency in the all treatment group. This analysis will be conducted for the 2 safety populations. A listing of SAEs will be provided.

The number and percentage of patients who permanently discontinued from study treatment due to an AE (including AEs that led to death) during the treatment period will be summarized by treatment using MedDRA PT. Events will be ordered by decreasing frequency in the all treatment groups. This analysis will be conducted for the 2 safety populations.

6.14.3. Clinical Laboratory Evaluation

As described more fully in compound level safety standards and in the laboratory-related PhUSE white papers (PhUSE 2013; PhUSE 2015), the clinical laboratory evaluations will be summarized with the following displays described in [Table AMAJ.6.8](#).

Table AMAJ.6.8. Summaries/Displays/Analysis for Clinical Laboratory Evaluations

Analysis	Population
Box plots of observed values (and change from baseline values) by visit. Change from baseline to last observation will be summarized within the box plot of changes (rightmost column), and descriptive summary statistics will be included in a table below the box plot along with a p-value using the ANCOVA model described in Section 6.14.	I, A ^a
Treatment-emergent abnormal high lab values (i.e., patients shifting from a normal/low maximum baseline value to a high maximum postbaseline value) or low lab values (i.e., patients shifting from normal/high minimum baseline value to a low minimum postbaseline value)	I, A
Scatter plot of maximum (minimum) postbaseline value vs maximum (minimum) baseline value	I, A
Shift tables showing the number of patients who shift from each category of maximum (minimum) baseline observation to each category of maximum (minimum) postbaseline observation. Here categories may be low, normal, or high with cut-offs defined in the compound level safety standards.	I, A

Abbreviations: A = All Active Treatment Safety; ANCOVA = analysis of covariance; I = Induction Safety.

^a Excluding placebo/250 miri treatment group for all active treatment safety population.

For these displays, the postbaseline periods will be identical to those described in Section 6.14.2. Postbaseline measurement for continuous analysis (for example, boxplots) will include *only* scheduled measurements, while postbaseline categorical analysis (for example, shifts) will include *both* scheduled and unscheduled measurements.

Measurements are defined to be in the baseline periods as follows:

- *Induction Safety Population:*
 - For analyses of continuous measurements: the last scheduled or unscheduled nonmissing measurement recorded during the Screening Period.
 - For analyses of categorical measurements: all scheduled or unscheduled nonmissing measurements recorded during the Screening Period.
- *All Active Treatment Safety Population:*
 - For analyses of continuous measurements: (1) the last scheduled or unscheduled nonmissing measurement recorded during the Screening Period for the patients randomized to mirikizumab and secukinumab, (2) the last scheduled or unscheduled nonmissing measurement recorded before first miri treatment for patients randomized to placebo.
 - For analyses of categorical measurements: (1) all scheduled or unscheduled nonmissing measurements recorded during the Screening Period for the patients randomized to mirikizumab and secukinumab, (2) the last scheduled or unscheduled nonmissing measurement recorded before first miri treatment for patients randomized to placebo.

For any lab given on the day of first taking study medication at the start of the postbaseline period, the start time of the study treatment will be used to determine whether the lab was pre-

versus postbaseline. If time for the lab is missing, it will be assumed to be in the baseline period (that is, we assume the protocol defined order of procedures was followed). Following the compound level safety standards, for some labs a safety concern may exist for only high (or only low) values. For these labs, displays with only maximum (or minimum) values will be used and shift tables will be presented accordingly.

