## Section 2: Schedule of Activities

Procedure a	ETV s	Follow-up Period t	
		V801	V802
Visit Number		V801	V802
Week		LV+4W	LV+12W
Day with Visit Tolerance Interval		29 ± 5	85 ± 5
Chest Radiography for TB Screeninge	X		
Investigator Completed Clinical Efficacy Scales			
Assessment of dermal symptoms	X		
Global improvement score	X		
Laboratory Tests			
HBV DNA testing n	X	X	X

Abbreviations: DNA = deoxyribonucleic acid; ETV = early termination visit; HBcAb = anti-hepatitis B core antibody; HBsAb± = hepatitis B surface antibody positive; HBV = hepatitis B virus; IP = investigational product; LV = last study visit; PCP = pneumocystis pneumonia; TB = tuberculosis; V = visit; W = weeks.

- a All activities should be completed prior to any study dose administration unless otherwise stated.
- b Visit 1 procedures may be conducted over more than 1 day as long as all tasks are completed within the allowable visit tolerance (at least 3 days should be allowed for receipt of laboratory test results).
- e Chest radiography will be performed locally at screening unless it has been performed within 3 months before initial screening (provided the radiographs and/or formal report are available for the investigator's review). In addition, chest radiography will be performed at Week 52, or for subjects who discontinue the study early if more than 12 weeks have elapsed since the previous study radiography was obtained. This radiography may be performed within 12 weeks if medically indicated. In the opinion of the investigator, if evaluating chest radiography is medically necessary, the investigator may do so any time during the study, including the follow-up period. For additional details, see revised Section 9.4.5.3 in Section 4.7 of the addendum.
- n Any enrolled patient who is HBcAb+ and/or HBsAb+ will undergo periodic monitoring of HBV DNA with HBV DNA testing (JSH 2017) (see revised Section 9.4.5.4 in Section 4.7 of the addendum). Any patient with a positive HBV DNA test at any time must be discontinued from the study and receive appropriate follow-up medical care, including consideration for antiviral therapy. (Refer to revised Section 9.4.5.4 in Section 4.7 of the addendum for further information regarding the timing of discontinuation).

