6.1.1.1. Study Time Intervals

[Table AMAJ.6.3](#) displays a list of study periods along with the definition of which patients will be considered to have entered the study period and when the individuals start and end the study period. The table shows both a date and a time.

To calculate the length of any time interval or time period in this study the following formula will be used:

$$\text{Length of interval (days)} = \text{End Date} - \text{Interval Start Date} + 1$$

Only for the purpose of calculating the length of study period time intervals, the words “prior to” in [Table AMAJ.6.3](#) should be understood to mean “the day before” while the words “after” should be understood to mean “the day after.”

To convert any time length from days to years, the following formula will be used:

$$\text{Length of interval (years)} = \text{Length of interval (days)} / 365.25$$

To convert any time length from days to weeks, the following formula will be used:

$$\text{Length of interval (weeks)} = \text{Length of interval (days)} / 7$$

Table AMAJ.6.3. Definition of Study Period Time Intervals

Study Period	Start Definition	End Definition
Screening: All patients who sign informed consent are considered as entering the Screening Period.	Informed consent date	Prior to the start of induction
Induction Period: All patients who are randomized to the study are considered as entering the Induction Period.	At the first injection following randomization date/time ^a . For patients who are randomized but not dosed, the Induction Period starts on the date of randomization.	Prior to the start of maintenance. For patients who discontinue before or on the Week 16 visit, the induction period ends at the last date of treatment discontinued date or last treatment visit date.
Maintenance Period: All patients who had any Week 16 to Week 52 visits (except the ones who discontinued the study at Week 16) are considered to have entered the Maintenance Period.	At the Week 16 dosing date/time. ^a If a patient is unable to be dosed at the Week 16 visit, the Maintenance Period starts at the Week 16 visit. If the patient misses the Week 16 visit, the Maintenance Period starts at Day 118.	After the Week 52 visit date. If patients discontinued prior to Week 52, the Maintenance Period ends at the last date of treatment discontinued or last treatment visit date.

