6.1.1.2. Definition of Study Baseline

For efficacy and health outcomes, study baseline is defined as the last nonmissing assessment (including unscheduled visits) before the first injection, which in most cases will be the measurement recorded at Week 0 (Visit 2). For efficacy/health outcome measures, if the patient does not take any injection, the last available value on or prior to randomization date will be used. In cases where baseline measurements are taken on the same day as injection, these measurements will be used as the baseline values for data analysis.

For the Psoriasis Symptoms Scale (PSS), the weekly average of at least 4 days of the consecutive 7 days prior to the first injection (or randomization, if the patient does not take any injection) will be the study baseline score.

Baseline for safety analysis is described in the safety section.

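### Imputing a missing dose time to the earliest possible time can class a timed pre-dose laboratory sample as postbaseline, against the order of procedures that SAP 6.14.3 itself assumes

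*SAP*

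**What the plan says.** Four rules in the SAP meet here, and one in the protocol.

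- **Period boundaries (SAP 6.1.1.1, Table AMAJ.6.3).** The Induction Period starts "At the first injection following randomization date/time" and the Maintenance Period starts "At the Week 16 dosing date/time". Both entries carry footnote a. Screening ends "Prior to the start of induction".
- **Missing dose time (same table, footnote a).** "Missing dose time will be imputed as the earliest time that is consistent with available data about dose time". The only example is a partial time: "suppose the minutes are missing but hour is present; in this case, we would impute the minutes to be 0".
- **Laboratory baseline (SAP 6.14.3).** Patients randomized to mirikizumab or secukinumab take their baseline from the Screening Period. In the All Active Treatment Safety Population, placebo patients take the last value before first mirikizumab.
- **Same-day samples (SAP 6.14.3).** On the day that opens the postbaseline period, the treatment start time decides on which side a sample falls. For a sample without a time: "If time for the lab is missing, it will be assumed to be in the baseline period". The stated reason is that the protocol's sequence is taken to have been followed.
- **Order of procedures (Protocol addendum, Schedule of Activities, footnote a).** "All activities should be completed prior to any study dose administration unless otherwise stated".

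Section 6.14.3 does not say what to do when the dose time is the one that is missing.

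**The concern.** A missing laboratory time and a missing dose time leave the same question open: was the sample drawn before or after the injection? Section 6.14.3 answers the first case with the order of procedures, so the sample is pre-dose. Footnote a answers the second by moving the dose as early as possible, so a timed sample tends to become post-dose. A correctly timed sample can therefore be handled worse than one with no time at all.

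At stake are the safety laboratory displays. An affected Week 0 value leaves the baseline, which falls back to an earlier screening value. For placebo patients who switch at Week 16, a value obtained on placebo can be counted as postbaseline on mirikizumab in the treatment-emergent, shift and scatter displays. The All Active Treatment box plots exclude that group (Table AMAJ.6.8, footnote a). Vital signs are to be summarized in a similar way (SAP 6.14.4), so they share the gap.

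**Working it through.** The plan states no figure on this point, so there is nothing to reproduce. The check applies the rules to constructed cases and then bounds the number of patients.

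**Step 1: the rules on test cases.** Assume a true dose at 09:40 and a sample drawn before it. Footnote a gives an imputed dose time of 09:00 if the minutes are missing. By the same wording it gives 00:00 if the whole time is missing. A sample is baseline if it has no time or if its time is earlier than the dose time used.

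| Sample time | Dose time known (09:40) | Minutes missing (09:00) | Wholly missing (00:00) |
|---|---|---|---|
| 09:10 | baseline | **postbaseline** | **postbaseline** |
| 08:50 | baseline | baseline | **postbaseline** |
| not recorded | baseline | baseline | baseline |

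Three of the nine pre-dose cases are misclassified. The untimed sample never is.

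**Step 2: how often missing minutes matter.** Assume that the dose minute is uniform over the hour and the sample is drawn L minutes before the dose. It is misclassified only if it falls in the same clock hour, so the share is (60 − L)/60 for L up to 60 and 0 beyond.

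- L = 5: 55/60 = 92%
- L = 15: 45/60 = 75%
- L = 30: 30/60 = 50%
- L = 45: 15/60 = 25%
- L = 60 or more: 0%

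With a wholly missing dose time, every timed pre-dose sample that day is misclassified.

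**Step 3: upper bound on patients.** The planned totals are 1443 randomized, of whom 111 to placebo (SAP 5.2). The share of dosing records with a missing time is not given, so 1% to 5% is an assumption.

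- Week 0 value lost from baseline: 0.01 × 1443 = 14.4, about 14; 0.05 × 1443 = 72.2, about 72.
- Placebo value counted on mirikizumab: 0.01 × 111 = 1.1, about 1; 0.05 × 111 = 5.6, about 6.

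These are ceilings. They take every missing time as wholly missing, every patient as having a timed same-day sample, and every randomized placebo patient as reaching the Week 16 dose.

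**Step 4: when a false flag follows.** Table AMAJ.6.8 counts a treatment-emergent high value only when the maximum baseline value was normal or low and the maximum postbaseline value is high, with the mirror rule for low values. A misplaced sample therefore creates a false flag only if it is abnormal and the baseline that remains was not already abnormal in that direction.

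**The case against.** **Rules held elsewhere.** Section 6.14.3 refers to compound-level safety standards for fuller detail, and these may deal with dose times. The protocol document here is the Japan addendum; the main protocol's laboratory schedule is not in it, and the addendum's own schedule lists no laboratory test at Week 0. This limits what can be said about frequency. It does not remove the conflict, because 6.14.3 itself foresees samples on the first-dose day and itself adopts the order-of-procedures assumption.

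**A kinder reading of footnote a.** The data used to impute could be taken to include the sample time together with the expected order. The wording and the example concern the dose time's own fields, so that reading is strained.

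**A conservative convention.** Assigning uncertain values to the treated period is common in safety work. It suits adverse events, where SAP 6.14.2 also sends a missing start time to the later period. For laboratory data, however, the SAP chose the opposite assumption and gave its reason.

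**Stronger readings that the documents do not support.**
- A reader might take 14 to 72 patients as an estimate. It is an upper bound on an assumed rate.
- A reader might infer that any abnormality present before dosing becomes treatment-emergent. Step 4 shows that it does not.
- A reader might infer bias between arms. At Week 0 the rule applies to every blinded arm alike.
- A reader might see a contradiction with efficacy, where for same-day values "these measurements will be used as the baseline values for data analysis" (SAP 6.1.1.2). That section says safety baseline is described separately, so this is a contrast only.
- A reader might think that every Week 16 shift matters. For patients on mirikizumab or secukinumab from Week 0, moving a sample across the Induction/Maintenance boundary changes nothing in the All Active Treatment analyses, which span both periods.

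**Conclusion.** Wrong as written, but minor. Footnote a and the same-day comparison in 6.14.3 together class a timed pre-dose sample as postbaseline when the dose time is wholly missing, or when only the minutes are missing and the sample falls in the same clock hour as the dose. This contradicts the assumption that 6.14.3 makes when the laboratory time is missing.

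The size is unknown and probably small: per 1% of dosing records with a missing time, no more than about 14 patients at Week 0 and about 1 placebo patient at Week 16. The Week 16 effect runs in one direction, since it charges placebo values to mirikizumab. No efficacy result is affected.

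The conclusion assumes that no rule outside these documents overrides footnote a for laboratory data, and that a wholly missing time is imputed to 00:00, which the footnote implies but does not illustrate.

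**What to change.** Keep footnote a for the period definitions in Table AMAJ.6.3. Add to SAP 6.14.3, and apply to vital signs in 6.14.4: when the dose time is missing or partial and the recorded times do not establish the order, a scheduled measurement on the dosing day is treated as pre-dose, and for these data this takes precedence over footnote a.

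The condition about order is needed. With a dose recorded in hour 09 and a sample at 14:00, the sample is plainly post-dose and should stay so. Restricting footnote a to adverse events would go too far, because the period starts would then have no dose-time rule for other data.

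Under this wording all nine cases in the table are classed as baseline. The cost is one sentence and one programming condition, with no new data. A count of dosing records with missing or partial times at Week 0 and Week 16 would show whether any patient is affected.
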